Randomization ^a		X												
Cytarabine – continuous infusion		X	X	X	X	X	X ^d	X ^d						100 mg/m ² /day (Note: FLT3-positive participants may receive 200 mg/m ² /day)
Idarubicin 12 mg/m ² /day OR Daunorubicin 60 mg/m ² /day		X	X	X ^d										
Study intervention – bolus		X												4 mg/kg via IV push, begin 30 min after anthracycline infusion ends
Study intervention – continuous infusion		X	X	X	X	X	X ^d	X ^d						0.25 mg/kg/hour; Begin after bolus dose
Adverse event assessments	Procedure-related SAEs	All AEs ----- →										X	Record through 42 days after start of the last induction or consolidation treatment cycle (regardless of completion or discontinuation)	
Concomitant medications	X	----- →										X		
Medical resource utilization		----- →										X		

Abbreviations: AE=adverse event; aPTT=activated partial thromboplastin time; CR=complete response; D=day; D14=Day 14 (only day specified within window); DC=discontinuation; ECG=electrocardiogram; ECOG=Eastern Cooperative Oncology Group; FISH=fluorescence in situ hybridization; HMGB1=high mobility group box protein 1; MRD=measurable residual disease; MUGA=multigated acquisition scan; PK=pharmacokinetics; PT/INR=prothrombin time/international normalized ratio; SAE=serious adverse event

Refer to footnotes on the next page

^a All prestudy/screening procedures (including cytogenetic and molecular analyses) will ideally be completed within 14 days of randomization. First dose of study intervention should be administered as soon as possible after randomization, and must be administered no more than 24 hours after randomization. Screening procedures do not need to be repeated prior to reinduction.

^b Bone marrow aspirate/biopsy will be performed once between approximately Day 14 and Day 21 (Day 22-23 for participants taking midostaurin), when peripheral blood is negative for persistent AML, to determine the need for reinduction. (If the ~Day 14 bone marrow is not evaluable or assessment of aplasia is equivocal, a repeat evaluation may be performed 5 to 14 days later, at the discretion of the investigator, in order to determine effect and need for second induction). Thereafter, additional bone marrow samples will be collected to confirm response/persistence/relapse after second induction and consolidation cycles. For participants who achieve CR/CRi, measurable residual disease assays will be performed by the central laboratory on the recovery marrow sample.

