3. OBJECTIVES AND ENDPOINTS

For definitions and response and outcomes criteria, refer to Section 8.2.2 and [Appendix 7](#).

Objectives	Endpoints
Primary Efficacy	

 To compare the efficacy of dociparstat plus standard chemotherapy versus standard chemotherapy alone as upfront treatment for newly-diagnosed AML 	
 Overall survival (OS).
Key Secondary Efficacy	

 To compare the efficacy of dociparstat plus chemotherapy versus chemotherapy alone with respect to event-free survival (EFS). 	
 EFS following CR. Defined as time from randomization to treatment failure, relapse, or death from any cause, whichever occurs first, with treatment failure defined as failure to achieve CR within 42 days of the start of induction (or start of reinduction, when applicable).
Secondary Efficacy	

 To compare the efficacy of dociparstat plus chemotherapy versus chemotherapy alone with respect to event- and relapse-free survival. 	
 EFS following CR/CRI, with treatment failure defined as failure to achieve CR/CRI within 42 days of the start of induction (or start of reinduction, when applicable). Relapse-free survival (RFS) after CR. RFS after CR/CRI.

 To compare MRD status with dociparstat plus chemotherapy versus chemotherapy alone. 	
 Proportion of participants who achieve CR with MRD_{neg}, as determined by multiparameter (multicolor) flow cytometry (MFC), at the end of induction and consolidation therapy. Proportion of participants who achieve CR/CRI with MRD_{neg}, as determined by MFC, at the end of induction and consolidation therapy. Proportion of participants who achieve MRD_{neg} (regardless of CR), as determined by MFC, at the end of induction and consolidation therapy. Association between CR with MRD_{neg} and relapse. Association between MRD_{neg} and relapse. Association between MRD_{neg} and OS.

 To compare post-induction response rates after treatment with dociparstat plus chemotherapy versus chemotherapy alone. 	
 Proportion of participants who achieve CR. Proportion of participants who achieve CR/CRI. Proportion of participants who achieve CR or complete remission with partial hematologic recovery (CRh).

Objectives	Endpoints

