Cumulative incidence of relapse	
Defined through 5 years after randomization only for participants achieving CR (or CR/CRi) during induction/reinduction.
 
Measured from the date of randomization to the date of relapse. Participants not known to have relapsed will be censored on the date they were last known to be alive. Participants who die without relapse will be counted as competing-risk events.

Overall survival (OS) *Primary Endpoint	
Defined for all study participants through 5 years after randomization.
 
Measured from the date of randomization to date of death from any cause.
 
Participants not known to have died at last follow-up contact will be censored on the date they were last known to be alive.

Event-free survival (EFS) following CR *Key Secondary Endpoint	
Defined for all study participants through 5 years after randomization.
 
Measured from the date of randomization to treatment failure, relapse, or death from any cause, whichever occurs first. For this endpoint, treatment failure is defined as failure to achieve CR within 42 days of the start of induction/reinduction. Participants not known to have relapsed or died will be censored on the date they were last known to be alive.

EFS following CRi	
Defined for all study participants through 5 years after randomization.
 
Measured from the date of randomization to treatment failure, relapse, or death from any cause, whichever occurs first. For this endpoint, treatment failure is defined as failure to achieve CRi within 42 days of the start of induction/reinduction. Participants not known to have relapsed or died will be censored on the date they were last known to be alive.

Relapse-free survival (RFS)	
Defined through 5 years after randomization only for participants achieving CR (or CR/CRi) during induction/reinduction.
 
Measured from the date of randomization to date of relapse or death from any cause. Participants not known to have relapsed or died at last follow-up contact will be censored on the date they were last known to be alive.

Time to recovery of neutrophil count	
Defined for all study participants.
 
Measured as time from date of randomization until the first day the ANC is $>500/\mu\text{L}$ and is $>1000/\mu\text{L}$ following induction or reinduction (if indicated).

Response / Outcome	Definition

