9.4.2. Key Secondary Endpoint

The key secondary EFS endpoint will be tested using the same method as the primary endpoint at two-sided alpha 0.01. A participant with any bone marrow CR assessment between Days 22 and 42, inclusive, after start of induction or reinduction treatment will be considered an induction success; relapse and death events will be assessed following the last CR assessment during this time period. A participant with no CR assessments during this window will be considered an induction failure and imputed as such at randomization. Participants with induction success and no observed relapse or death events will be censored at the time they were last known to be alive. Maximum neutrophil and platelet counts within 7 days before or after the bone marrow draw will be used to determine count recovery. The key secondary analysis will be supplemented by a planned sensitivity analysis (not subject to alpha control), in which participants progressing to hematopoietic cell transplant will be censored at the time of transplant. The key secondary analysis will be conducted at the same time as the final primary OS analysis.

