9.4.3. Other Secondary Endpoints

In the event that both the primary and key secondary analysis rejects the null hypothesis, the secondary analyses of MRD_{neg}, time to platelet recovery, time to neutrophil recovery, and CR will be tested in a fixed sequential manner at two-sided alpha 0.05. If the primary analysis rejects the null hypothesis while the key secondary does not, these secondary analyses will be tested in a fixed sequential manner at two-sided alpha 0.04; similarly, if the key secondary analysis rejects the null hypothesis while the primary analysis does not, these secondary analyses will be tested in a fixed sequential manner at two-sided alpha 0.01. No other multiplicity adjustments will be made for secondary analyses.

Time-to-event secondary analyses will use the same methods used for the primary and key secondary analyses.

Dichotomous secondary efficacy analyses will be analyzed using a Cochran-Mantel-Haenszel test stratified by each of the stratification factors. Number of successes/failures and success/failure rates will be presented for each treatment arm. Cochran-Mantel-Haenszel p-values, estimated common odds ratios, and corresponding approximate 95% CIs will be presented for each comparison. The Breslow-Day test will be used to test the homogeneity of the odds ratios across the strata. Missing data will generally be imputed as failure unless specifically defined otherwise in the SAP.

Cumulative incidence of relapse will be analyzed with death as a competing risk adjusted for baseline strata, with corresponding cumulative incidence plots, Fine-Gray models, and cause-specific and sub distribution hazard ratios with corresponding 95% CIs.

OS, EFS, and MRD will be analyzed by various subgroups, including, but not limited to, each of the stratification factors, anthracycline use, sex, and race (each race contributing >10% to the study plus other races grouped). OS and relapse will be analyzed by number of consolidation cycles. Multivariate modelling to assess the impact of these factors on key endpoints will be considered and defined in the SAP.

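### RFS and cumulative incidence of relapse are labelled as after CR and limited to responders, but timed from randomization, so each responder's time includes about 0.7 to 2.8 months in which no event can occur

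*Combined protocol and SAP*

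**What the plan says.** Section 3 names the endpoint "Relapse-free survival (RFS) after CR", with a CR/CRi version, and names cumulative incidence of relapse in the same way. Table 7 in Section 8.2.2 restricts both: "Defined through 5 years after randomization only for participants achieving CR (or CR/CRi) during induction/reinduction". It then sets the origin. RFS is "Measured from the date of randomization to date of relapse or death from any cause" and cumulative incidence of relapse is "Measured from the date of randomization to the date of relapse". Appendix 7 repeats the randomization origin for both.

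Table 7 recognizes relapse only once CR or CRi has been achieved. For EFS, Section 9.4.2 treats as an induction success a participant with "any bone marrow CR assessment between Days 22 and 42, inclusive, after start of induction or reinduction treatment", and states that "relapse and death events will be assessed following the last CR assessment during this time period". Section 9.4.3 adds: "Time-to-event secondary analyses will use the same methods used for the primary and key secondary analyses". Those methods include medians and Kaplan-Meier estimates every 90 days (Section 9.4.1). Table 1, footnote a, requires that the first dose of study intervention "must be administered no more than 24 hours after randomization".

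**The concern.** A participant enters the RFS or relapse-incidence analysis only by surviving to a documented remission. The interval from randomization to that remission is therefore event-free by construction, but it is counted as relapse-free time. It is longest for those who needed reinduction. OS and EFS do not have this problem, because Table 7 defines them for all participants and an early death or induction failure counts.

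At stake are the absolute figures: medians, 90-day Kaplan-Meier estimates and relapse-incidence curves. A reader who takes the label at face value will read them as time after remission, which they are not. Section 2.1 names RFS beside OS as an outcome that dociparstat is expected to improve, so the figures are likely to be cited.

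**Working it through.** **The plan's own figure.** There is none for RFS or relapse incidence: no median, rate, event count or power. The OS design figure does reproduce. With 308 events, HR 0.7 and two-sided alpha 0.04, power is Φ(√(308/4) × |ln 0.7| − 2.054) = Φ(3.130 − 2.054) = 85.9%, against the stated >85%. Nothing below alters it.

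**Inputs from the documents.** CR is assessed on Days 22-42 of induction or reinduction (9.4.2). First dose is at most 1 day after randomization (Table 1). Reinduction follows a Day 14-23 marrow (4.1) or the Day 22-42 response assessment (4.3).

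**Built-in event-free time, at 30.44 days per month.**

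| Route to CR | Days from randomization | Months |
|---|---|---|
| One induction | 21 to 42 | 0.7 to 1.4 |
| Reinduction after Day 14-23 marrow | 14+21 = 35 to 23+42 = 65 | 1.2 to 2.1 |
| Reinduction after a Day 42 assessment | up to 42+42 = 84 | up to 2.8 |

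**Average (assumed).** Take CR evenly spread over the window, mean (21+42)/2 = 31.5 days, and reinduction starting on average (14+23)/2 = 18.5 days later.
- None reinduced: 31.5 days = 1.03 months.
- 20% reinduced: 31.5 + 0.2 × 18.5 = 35.2 days = 1.16 months.
- 30% reinduced: 31.5 + 0.3 × 18.5 = 37.1 days = 1.22 months.

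The result depends on when CR is documented. If every CR falls at Day 22 and reinduction starts at the earliest (35 days in all), the mean is 21 days (0.69 months) with no reinduction and 0.8 × 21 + 0.2 × 35 = 23.8 days (0.78 months) with 20%. The share reinduced would have to reach (30.44 − 21)/(35 − 21) = 67% for the mean to pass one month. If every CR falls at the end of the window, the mean is 42 days (1.4 months) with no reinduction, and 0.8 × 42 + 0.2 × 65 = 46.6 days (1.5 months) with 20%.

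**Effect on RFS estimates.** Assume exponential RFS from CR with median m. Survival from CR is S(t) = exp(−t ln 2/m); timed from randomization with mean shift g it is close to exp(−(t − g) ln 2/m). With g = 1.16 months:

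| Median from CR (months) | Median from randomization (months) | 12-month RFS, CR origin | 12-month RFS, randomization origin |
|---|---|---|---|
| 10 | 11.2 | 43.5% | 47.2% |
| 15 | 16.2 | 57.4% | 60.6% |
| 20 | 21.2 | 66.0% | 68.7% |

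The gain at 12 months is 2.7 to 3.7 points. It is larger at the first 90-day estimate (2.96 months): for m = 10, 81.5% becomes 88.3%.

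**Relapse incidence.** At any fixed time, RFS = 1 − incidence of relapse − incidence of death without relapse. The later clock lowers both incidences, so relapse incidence is understated by at most the RFS gain.

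**Hazard ratio.** In a simulation of 20,000 per arm, with exponential RFS from CR and censoring at 36 months, equal pre-CR time leaves 0.697 at 0.697. Reinduction of 30% (control) versus 20% moves it by less than 0.01 (0.714 to 0.718). CR reached 5 days earlier on dociparstat moves it by about 0.01 (0.702 to 0.710). A separate simulation with 40% versus 20% reinduced moves a null hazard ratio by 0.01-0.02.

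**The case against.** The strongest reply is that the origin is a stated choice. Table 7 and Appendix 7 agree, Section 9.4.1 also starts survival time at randomization, and a median reported as time from randomization is correct as defined. The after-CR label could be read as naming only the population. Randomization is also the one origin that treatment cannot shift. The recovery marrow follows count recovery (Table 1, footnote c), and count recovery is itself a tested secondary outcome, so a CR-date origin could move earlier on dociparstat and lengthen RFS without delaying any relapse. Finally, RFS and relapse incidence are outside the fixed sequence in Section 9.4.3 and feed no interim rule.

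Most of this stands. It limits the harm to absolute estimates and is a reason to keep the randomization-origin analysis. It does not remove the mismatch between a label that refers to time after remission, a set that conditions on remission, and a clock that starts before it.

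Three stronger readings are tempting, and the documents support none of them. A reader might infer that RFS is overstated by more than a month as a fixed fact; the plan gives no time-to-CR distribution or reinduction rate, and CR at Day 22 after one induction adds only about 0.7 months. A reader might infer a biased arm comparison; sizeable imbalances between arms move the hazard ratio by no more than about 0.02. A reader might infer that the plan contradicts itself on the origin; it states the same origin throughout.

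**Conclusion.** The point holds as a mismatch between label and definition that affects descriptive estimates. The range of built-in time (0.7-1.4 months after one induction, 1.2-2.8 months after reinduction) follows from the protocol windows. The average effect of about 1.2 months on medians and about 3-4 points on 12-month RFS rests on three assumptions: CR evenly spread over Days 22-42, 20-30% reinduced, and exponential RFS with a median of 10 to 20 months from CR. The arm comparison is nearly unaffected, and no confirmatory test or design quantity changes. This is a minor but worthwhile correction.

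**What to change.** In Table 7 and Appendix 7, measure RFS and cumulative incidence of relapse from the date of first documented CR (or CR/CRi). Define that date as the date of the qualifying marrow, with counts taken within 7 days either side. State that relapse and death are counted from that same date. Otherwise the EFS rule in Section 9.4.2, which counts events after the last CR assessment in the window, could carry over through Section 9.4.3 and leave event-free time between the first and last assessments.

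Keep the randomization-origin analysis, labelled as such, as a sensitivity analysis, because the CR date can shift with the speed of count recovery. Add a sentence that the arm comparisons of these two endpoints are descriptive, since the set is defined by an outcome after randomization. Changing the origin does not cure that, and Section 9.3 assigns all efficacy endpoints to the ITT set.

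The cost is wording in two tables, one derivation rule and one extra analysis. Marrow results (8.2.1) and laboratory results (8.3.4) already go into the eCRF, so no new data are needed.

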8.2.3. Long-Term Follow-up

After completion or discontinuation of study intervention, participants will be followed-up until death or for 5 years after randomization. Contact with the participant (or caregiver or treating physician, as applicable) will be made every 3 months for the first 24 months, then every 6 months for the remaining follow-up period.

At (suspected) relapse, a full bone marrow examination should be performed, including morphology, cytogenetics, and biobanking; also collect peripheral blood for immunological phenotyping, molecular diagnostics, and biobanking. Participants will be asked to notify the study center in the event of relapse, even if a different physician/institution will be handling their future care.

The following information will be collected as applicable: disease status (relapse date) (may include results of tests used for diagnosis of recurrence), death date, cause of death, and related source documentation. In addition, all AML therapies (i.e., for the treatment of AML and/or prevention of relapse) will be collected from 43 days after start of the last treatment cycle through the time of last study follow-up; this includes HCT and/or CAR T cell date(s) and details, other chemotherapy agent start/stop dates (and reasons for the treatment choice), and maintenance therapy start/stop dates.

8.3. Safety Assessments

Planned time points for all safety assessments are provided in the Schedule of Activities/Assessments (see [Table 1](#) and [Table 2](#)).

The investigator will discuss any immediate safety concerns with the sponsor (or designee) upon occurrence or awareness to determine if the participant should continue or discontinue receiving study intervention.

Safety data will be monitored by an independent DMC on a routine basis (see Section [9.6](#)).

8.3.1. Physical Examinations

Measure height at screening; measure weight (without shoes) at screening and at the start of consolidation therapy.

Determine ECOG status (see [Appendix 5](#) for details) at screening and confirm status at baseline before the first dose of study intervention.

Complete a physical examination at screening as part of the review for eligibility for the study. Investigators should pay special attention to clinical signs related to AML and any other previous or ongoing serious illnesses. Record any clinically-relevant findings in the eCRF as medical history.

During the treatment period of the study (i.e., after the first dose of study intervention), record any clinically-relevant change(s) in physical examination (obtained during routine standard of care) findings in the eCRF as an AE(s).

8.3.2. Vital Signs

Assess all vital signs (temperature, pulse rate, respiratory rate, and blood pressure) at screening as part of the review for study eligibility. Record any clinically-relevant findings as medical history in the eCRF.

During the treatment period of the study, record any clinically-relevant change(s) in vital sign measurements (obtained during routine standard of care) in the eCRF as an AE(s).

8.3.3. Electrocardiograms

ECGs will be obtained using an ECG machine that automatically calculates the heart rate and measures PR, QRS, QT, and QTc intervals.

As specified in the Schedule of Activities, 12-lead ECGs will be obtained at the following time points:

- Screening
- Baseline/Day 1 predose
- Day 1 at the end of the study intervention (i.e., dociparstat or placebo) bolus dose
- Day 8 at the end of the study intervention (i.e., dociparstat or placebo) infusion for the initial induction cycle
- Additional readings may be necessary to monitor AEs and/or changes in ECG measurements (e.g., as described in Section 7)

At screening, 3 individual ECG tracings should be obtained as closely as possible in succession, but ideally no more than 2 minutes apart, with the full set of triplicates completed in less than 4 minutes. At subsequent time points, a single ECG tracing will be obtained, with a repeat tracing to confirm QTc intervals >480 msec.

Refer to Section 5.2 for QTc-related criteria for participant exclusion and Section 7 for QTc-related criteria for interruption and discontinuation of study intervention.

At screening, as part of the review for eligibility for the study, and at baseline prior to the first dose of study intervention, record any clinically-relevant ECG findings as medical history in the eCRF. During the treatment period of the study, record any clinically-relevant change(s) in ECGs (obtained at protocol-specified time points or during routine standard of care) in the eCRF as an AE(s).

It is recommended that QTc be calculated using Fridericia's formula (QTcF) for all participants. If a study center does not have access to an ECG machine capable of calculating QTcF, then correction using an alternate formula may be used. All recordings for a single participant must use the same correction formula; therefore, if one formula is used at screening to determine eligibility for enrollment, that same formula must also be used during treatment to determine if criteria have been met for interruption or discontinuation of study intervention.

